6.3.1 Primary endpoint

6.3.1.1 Primary efficacy analysis based on on-treatment strategy

The primary objective of this study is to assess the efficacy of fitusiran on prevention or reduction of bleeding. Including bleeding events in the period of intercurrent events such as use of prophylactic medication or surgery or after fitusiran treatment discontinuation could significantly bias fitusiran effect and make the comparisons difficult to interpret. The on-treatment strategy is considered of greatest relevance in assessing this primary objective (ICH E9 (R1), 2018). The primary efficacy analysis population will be the ITT Analysis Set as defined in [Section 4](#).

Global Protocol

The number of bleeding episodes will be annualized for each patient using the following formula:

$$\text{Annualized bleeding rate (ABR)} = \frac{\text{total number of bleeding episodes}}{\text{total number of days in the respective period}} \times 365.25.$$

The primary efficacy analysis will include all bleeding episodes occurring in the efficacy period.

Let λ_F represent the ABR for fitusiran arm and λ_O represent the ABR for on-demand arm. The null and alternative hypotheses of the primary analysis, respectively, can be written as follows:

$$H_0: \frac{\lambda_F}{\lambda_O} = 1 \quad H_A: \frac{\lambda_F}{\lambda_O} \neq 1$$

An estimated ABR ratio $\frac{\lambda_F}{\lambda_O} < 1$ and two-sided p-value < 0.05 from the significance test will lead to the rejection of H_0 in favor of H_A ; it will be concluded that prophylactic use of fitusiran reduces the frequency of bleeding episodes compared to the on-demand therapy.

The ABR ratio λ_F/λ_O will be estimated using a negative binomial model:

$$\begin{aligned} & \log(\text{number of bleeding episodes}) \\ &= \beta_0 + \beta_1 \cdot \text{Treatment} + \beta_2 \cdot \text{ABR}_0 + \beta_3 \cdot \text{Hemophilia type} + \log(\text{duration}). \end{aligned}$$

The number of bleeding episodes is the response variable. The treatment arm, randomization strata of number of bleeding episodes in the 6 months prior to study entry (ABR_0) and randomization strata of hemophilia type are treated as fixed effects. The logarithm of the duration (in years) that each patient spends in the efficacy period matching the bleeding episode data being analyzed is included as an offset variable to account for unequal follow-up time due to early withdrawal, surgery, etc.

The ratio of ABR in the fitusiran treatment arm to the on-demand arm, its 95% CI, and the p-value for the hypothesis above will be presented. The estimated mean ABRs in the 2 treatment arms along with their 95% CIs from the model will be presented. In addition, median and interquartile range (Q1, Q3) for the observed ABR will be summarized descriptively by treatment arm.

For patients who don't have bleeding episode data collected after Day 28 (eg, due to early study discontinuation), the available bleeding episode data starting from Day 1 will be used in the primary analysis. A summary of missing data pattern by treatment arm will be provided. To evaluate the impact from this single imputation, a sensitivity analysis will be performed based on imputed bleeding data in the efficacy period using multiple imputation (MI) method as described in [Section 6.3.1.2](#) below.

US Protocol

The number of bleeding episodes will be annualized for each patient using the following formula:

$$\text{Annualized bleeding rate (ABR)} = \frac{\text{total number of bleeding episodes}}{\text{total number of days in the respective period}} \times 365.25.$$

The primary efficacy analysis will include all bleeding episodes occurring in the treatment period.

Let λ_F represent the ABR for fitusiran arm and λ_O represent the ABR for on-demand arm. The null and alternative hypotheses of the primary analysis, respectively, can be written as follows:

$$H_0: \frac{\lambda_F}{\lambda_O} = 1 \quad H_A: \frac{\lambda_F}{\lambda_O} \neq 1$$

An estimated ABR ratio $\frac{\lambda_F}{\lambda_O} < 1$ and two-sided p-value < 0.05 from the significance test will lead to the rejection of H_0 in favor of H_A ; it will be concluded that prophylactic use of fitusiran reduces the frequency of bleeding episodes compared to the on-demand therapy.

The ABR ratio λ_F/λ_O will be estimated using a negative binomial model:

$$\begin{aligned} & \log(\text{number of bleeding episodes}) \\ &= \beta_0 + \beta_1 \cdot \text{Treatment} + \beta_2 \cdot \text{ABR}_0 + \beta_3 \cdot \text{Hemophilia type} + \log(\text{duration}). \end{aligned}$$

The number of bleeding episodes is the response variable. The treatment arm, randomization strata of number of bleeding episodes in the 6 months prior to study entry (ABR_0) and randomization strata of hemophilia type are treated as fixed effects. The logarithm of the duration (in years) that each patient spends in the treatment period matching the bleeding episode data being analyzed will be included as an offset variable to account for unequal follow-up time due to early withdrawal, surgery, or etc.

The ratio of ABR in the fitusiran treatment arm to the on-demand arm, its 95% CI, and the p-value for the hypothesis above will be presented. The estimated mean ABRs in the 2 treatment arms along with their 95% CIs from the model will be presented. In addition, median and interquartile range (Q1, Q3) for the observed ABR will be summarized descriptively by treatment arm.

Given that the primary analysis is based on on-treatment strategy, primary and secondary bleeding-related data during the efficacy and treatment periods are expected to be complete. No sensitivity analysis about the missing data mechanism will be performed.

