5. SELECTION AND WITHDRAWAL OF PATIENTS

5.1. Inclusion Criteria

Each patient must meet all of the following inclusion criteria to be eligible for enrollment in the study:

1. Males \geq 12 years of age.
2. Severe hemophilia A or B without inhibitors evidenced by:
 - a. A central laboratory measurement or documented medical record evidence of FVIII $<$ 1% or FIX level \leq 2% at Screening.
 - b. On-demand use of factor concentrate to manage bleeding episodes for at least the last 6 months prior to Screening, and meet each of the following criterion:
 - Nijmegen modified Bethesda assay inhibitor titer of $<$ 0.6 BU/mL at Screening
 - No use of BPAs to treat bleeding episodes for at least the last 6 months prior to Screening
 - No history of immune tolerance induction therapy within the last 3 years prior to Screening
3. A minimum of 6 bleeding episodes requiring factor concentrate treatment within the last 6 months prior to Screening.

-
4. Willing and able to comply with the study requirements and to provide written informed consent and assent in the case of patients under the age of legal consent, per local and national requirements.

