7.1. Screening/Baseline Assessments

An informed consent form (ICF) or assent form that has been approved by the appropriate Institutional Review Board (IRB)/Independent Ethics Committee (IEC) must be signed by the patient (or legal guardian) before the Screening/Baseline procedures are initiated. All patients (or their legal guardians) will be given a copy of the signed and dated ICF and/or assent form.

Patient demographic and medical history will be obtained at Screening. Medical history must include documentation of factor concentrate prescriptions (in the medical or pharmacy record) and documentation of reported number of bleeding episodes over the last 6 months. Patients will

be screened to ensure that they meet all of the inclusion criteria and none of the exclusion criteria. Rescreening of patients is permitted with consultation of the study Medical Monitor.

To complement medical records, information regarding health resource use will be collected as specified in the Schedule of Assessments (Table 1), including days missed from work/school (as appropriate) and days not able to perform normal activities outside of work/school due to hemophilia, physician office visits, hemophilia treatment site visits, emergency room visits (reason and number), hospitalizations (reason, dates of hospitalization and associated length of stay).

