8.2.5.1. Primary Endpoint

The primary analysis will be performed on the ITT Analysis Set and will include all bleeding episodes occurring in the efficacy period (Day 29 to Day 246) including bleeding episode data collected after discontinuation of IMP. If a patient does not have bleeding episode data collected after Day 28 (eg, due to early study discontinuation), the available bleeding episode data starting from Day 1 will be used as bleeding episode data of the fitusiran period in the primary analysis. To avoid confounding the treatment effect, bleeding episode data during and after major surgery, AT administration, major trauma, or initiation of prophylaxis treatment with factor concentrates will be excluded from the primary analysis.

The number of bleeding episodes will be analyzed using a negative binomial model with fixed effects of treatment arm and the number of bleeding episodes in the 6 months prior to study entry (≤ 10 vs > 10) and hemophilia type (hemophilia A or B). The logarithm number of days that each patient spends in the efficacy period matching the bleeding episode data being analyzed will be included as an offset variable to account for unequal follow-up time due to early withdrawal or surgery. The p-value comparing bleeding rates in the 2 treatment arms and the ratio of bleeding rates in the fitusiran treatment arm to the on-demand arm along with its 95% CI will be presented. The estimated mean ABRs in each of the 2 treatment arms along with their 95% CIs will be presented from this model. In addition, summary statistics for ABR, including median and interquartile range, will be presented for each treatment arm, where ABR is defined as:

$$\frac{\text{total number of qualifying bleeding episodes}}{\text{total number of days in the respective period}} \times 365.25$$

Patients who discontinue treatment during the study will be encouraged to continue recording bleeding episode data.

Sensitivity analyses will be performed to evaluate the impact of missing data under different missing data mechanisms and details will be specified in the statistical analysis plan.

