2.2 Randomization methodology

Patients are randomized 2:1 to the fitusiran treatment arm and the on-demand arm. Randomization is stratified by the number of bleeding episodes in the 6 months prior to Screening (≤ 10 vs > 10) and hemophilia type (hemophilia A or B).

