5 GENERAL STATISTICAL METHODS

5.1 Sample size justification

Assuming a mean ABR of 18 with standard deviation (SD) = 14 in the on-demand arm (patients randomized to receive on-demand factor concentrates) and a mean ABR of no more than 4 with SD = 6 in the fitusiran treatment arm (patients randomized to receive fitusiran) in either the efficacy period or treatment period, with a sample size of 32 evaluable patients in on-demand arm and approximately 64 evaluable patients in the fitusiran treatment arm, it is projected that the study will have greater than 90% power for testing treatment difference in mean ABRs. This power estimation was based on negative binomial regression model with a 2-sided Type I error rate of 0.05.

The planned sample size is 120 randomized patients assuming a 20% drop-out rate.

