6.2 Demographics and baseline characteristics

Demographic and baseline characteristics, baseline disease characteristics, and medical history information will be summarized by treatment arm and overall for the ITT analysis set, safety analysis set (if different from the ITT analysis set), and the per-protocol analysis set. No formal statistical comparisons will be performed.

Age, height, weight, and body mass index (BMI) will be summarized using descriptive statistics. Age group, sex, race, ethnicity, and region will be summarized by presenting the numbers and percentages of patients in each category.

The following baseline disease characteristics will be summarized: age at diagnosis, time from diagnosis to randomization, hemophilia type, and number of bleeding episodes in the last 6 months prior to the study.

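### The bleeding-rate models adjust for prior bleeding only through the two-level stratum (≤10 vs >10), although the exact 6-month count is on record; adding it would bring a modest, uncertain gain in precision

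*SAP*

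**What the plan says.** Randomization: SAP 2.2 states that "Randomization is stratified by the number of bleeding episodes in the 6 months prior to Screening", cut at ≤10 vs >10, together with hemophilia type.

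Primary model: protocol 8.2.5.1 specifies a negative binomial model with "fixed effects of treatment arm and the number of bleeding episodes in the 6 months prior to study entry", at the same cut, and hemophilia type. SAP 6.3.1.1 writes the term as ABR_0, which looks like a rate, but defines it as the "randomization strata of number of bleeding episodes in the 6 months prior to study entry". The same model is given for the US protocol. SAP 6.3.2.1 to 6.3.2.3 repeat the analyses for the secondary bleeding rates, and SAP 6.3.1.4 repeats them by subgroup.

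The count itself: protocol 7.1 requires "documentation of reported number of bleeding episodes over the last 6 months", and SAP 6.2 lists the "number of bleeding episodes in the last 6 months prior to the study" among the baseline characteristics to be summarized. Eligibility (protocol 5.1) requires "A minimum of 6 bleeding episodes requiring factor concentrate treatment within the last 6 months prior to Screening", so the lower stratum holds counts of 6 to 10 and the upper stratum has no ceiling.

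Other models: SAP 6.3.2.4 (Haem-A-QoL), 6.3.3.4 (Haemo-QOL), 6.4.1 (antithrombin) and 6.4.2 (peak thrombin) each include both strata and the continuous baseline value of the outcome.

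**The concern.** Past bleeding frequency is the natural baseline counterpart of the primary outcome. Cutting it in two discards information: a patient with 11 prior bleeds is treated like one with 40. If past and on-study bleeding are correlated, the intervals for the rate ratio and the arm-specific ABRs are wider than they need be. The SAP adjusts for the continuous baseline in its other models and gives no reason for not doing so here.

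The gap is sharpest in the prior-bleed subgroups of SAP 6.3.1.4. Within ≤10 or >10 the stratum is constant, so those fits have no adjustment for prior bleeding at all.

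**Working it through.** **1. The plan's own figure.** SAP 5.1: "Assuming a mean ABR of 18 with standard deviation (SD) = 14 in the on-demand arm" and "a mean ABR of no more than 4 with SD = 6 in the fitusiran treatment arm", with 32 and 64 evaluable patients and two-sided alpha 0.05.

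Var(log ratio) = (SD₀/mean₀)²/n₀ + (SD₁/mean₁)²/n₁ = (196/324)/32 + (36/16)/64 = 0.0189 + 0.0352 = 0.0541, so SE = 0.2325. With log(4/18) = −1.504, |z| = 6.47 and power exceeds 99.9%. The stated >90% is reproduced as a conservative floor, and 96/0.8 = 120 is exact.

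**2. What the cut keeps.** The documents give no distribution for the prior count. Two were assumed, both truncated at 6: median 11 with 51% above 10, and median 14 with 71% above 10. The correlation of the stratum with the log count was 0.82 and 0.74, so the stratum keeps 0.82² = 67% or 0.74² = 55% of the log-count variance.

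As a rough guide that ignores Poisson noise, the SE ratio (stratum over log count) is √[(1 − ρ²r²)/(1 − ρ²)]. Here ρ is the correlation of log prior count with log on-study rate, and r² is the share kept. At ρ = 0.5 and r² = 0.67 this is √[(1 − 0.25 × 0.67)/0.75] = √(0.8325/0.75) = 1.05.

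**3. Simulation, stratum versus log count.** 1000 trials per scenario, 32/64 patients, follow-up 218 days (Day 29 to Day 246), ABR means and SDs from SAP 5.1, and allocation stratified at 10. Assumed: ρ, the two count distributions, and a prior-count slope either common to the arms or scaled to each arm's SD. The truth was linear in the log count, which favours the covariate.

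| ρ | Model SE ratio | Reduction = 1 − 1/ratio | Empirical SD ratio |
|---|---|---|---|
| 0 | 0.998 | −0.2% | 0.993–1.003 |
| 0.3 | 1.005–1.014 | 0.5–1.4% | 1.004–1.032 |
| 0.5 | 1.020–1.055 | 2.0–5.2% | 1.031–1.103 |
| 0.7 | 1.051–1.143 | 4.9–12.5% | 1.080–1.217 |

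At the planned ratio of 0.222, power was 100% with every model. At ρ = 0.5 (common slope, median 11) the 95% interval is about 0.151–0.327 with the stratum and 0.152–0.324 with the log count. In the most favourable scenario (ρ = 0.7, scaled slope, median 14) it is 0.152–0.324 against 0.160–0.309. At a much weaker ratio of 0.5 (common slope), power was 90.6–91.6% against 90.8–91.8% at ρ = 0.3, and 93.2–93.9% against 96.1–97.0% at ρ = 0.7.

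**4. Adding the count to the strata.** This is the change proposed, and it gains slightly less than replacing the stratum.

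- With arm SDs matched to SAP 5.1, the model SE rose 0.4% at correlation 0. It fell about 1% at 0.3, 3% at 0.5, 5% at 0.7 and 10% at 0.85.
- A second set of runs, also matched to SAP 5.1, gave a 5% cut at 0.5 in both arms. The cut shrank to 1.7% with 0.5 on-demand and 0.2 fitusiran, and to 0.8% with 0.5 and 0. For the 0.5/0.2 case the first set gave under 1%.

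**5. The >10 subgroup.** Assuming 16 and 32 patients, log-rate SD 0.75 and latent log-rate correlations of 0, 0.5, 0.7 and 0.85 (300 trials each), the covariate cut the SE by 0%, 5%, 10% and 19%. Power at an assumed ratio of 0.5 went from 74 to 74%, 80 to 82%, 85 to 92% and 91 to 97%.

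**6. Type I error.** Under the null, at correlations 0, 0.5 and 0.7, rejection rates for the two models were 7.3 and 7.0%, 9.3 and 9.0%, and 9.0 and 9.3%. Both exceed 5% in these small simulations. The covariate makes no visible difference.

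**The case against.** The term in the plan is prespecified, agrees between protocol and SAP, and is the factor used in the randomization. Nothing is inconsistent, and no primary decision turns on it. The prior count is retrospective and reported, whereas the outcome comes mainly from the eDiary under a 72-hour rule, with only treated bleeds counted (SAP 6.3). A log-linear term imposes a shape on a skewed count truncated at 6. By the arithmetic above, the fitusiran arm supplies 0.0352/0.0541 = 65% of the variance, and there an effective prophylaxis may weaken the link with past bleeding. The model is also written into the protocol, and the SAP is already at version 3.

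Much of this stands as a limit on size. It does not defeat the change. The strata stay in the model, so the match to the randomization is kept. The stratum is cut from the same reported history, so it carries the same reporting error. A mis-specified baseline covariate does not confound a randomized comparison. SAP 2.3 withholds efficacy summaries by arm from the sponsor until formal reporting, so the covariate can still be fixed before database lock.

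A reader might infer that the count is free precision and can never hurt. That is not supported. At correlation 0 the fitted SE was larger with the added covariate in 50% of simulated trials, and at 0.3 in 28%, although the average change was trivial. A reader might also infer that spontaneous and joint bleeding rates gain most. The documents give no power for those endpoints, and the recorded count covers bleeds of all kinds, so its value for predicting those types is unknown.

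**Conclusion.** The point holds as a modest efficiency improvement. It is not an error in the plan. The bleeding-rate models leave out a collected baseline value of the kind the SAP uses in its other adjusted models.

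The size rests on a correlation and a prior-count distribution that the documents do not give. The stratum-only SE is about equal at correlation 0, about 1% larger at 0.3, 2–5.5% larger at 0.5 and 5–14% larger at 0.7. When the count is added to the strata, the cut is about 3–5% at 0.5, and under 2% if the link is weak in the fitusiran arm. Savings well above 10% in the full trial need a very high correlation in both arms.

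A reader might conclude that the primary comparison is at risk. It is not: at the planned effect its power is essentially 100% with any of these models. What is at stake is interval width and, possibly, the secondary and >10-bleed subgroup analyses.

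**What to change.** Before database lock, add one line to SAP 6.3.1.1, carried through 6.3.2.1 to 6.3.2.3 and 6.3.1.4: keep both randomization strata and include the natural log of the 6-month bleed count as a covariate. Define the count over the 6 months before Screening, the window used for eligibility and randomization, since the SAP also words it as before study entry. If the primary model is to stay as it is, make this a named supportive analysis with its form fixed in advance. SAP 6.3.1.4 allows fits with as few as 3 patients per arm; state that the covariate is dropped where the model does not converge.

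The cost is one extra parameter, a log-linear assumption for a retrospective count, and a trivial loss of precision if the correlation is near zero. No new data are needed. The recorded count would also allow a check of the strata as randomized, since SAP 4 lists incorrect stratification data among the per-protocol deviations.

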6.3.1.2 Efficacy analysis based on treatment policy strategy

A supportive efficacy analysis will be performed by including all bleeding episodes collected through the end of the study, regardless of any premature treatment discontinuation, excluding only events due to major or minor surgeries based on ITT Analysis Set as in the primary analysis. The same negative binomial model as in the primary analysis will be used. It assesses the benefits of the fitusiran treatment policy strategy relative to on-demand treatment.

A sensitivity analysis to the above treatment policy analysis will be performed by including all bleeding events (ie, not excluding bleeding events due to surgeries).

Missing data sensitivity analyses using controlled imputation

The above efficacy analysis assumes the uncollected bleeding events after study discontinuation are missing at random (MAR). Sensitivity analyses will be performed to assess the robustness of this treatment policy analysis by imputing the missing data based on different missing data mechanism. The missing data will be imputed using multiple imputation (MI) methods for recurrent event data based on pattern mixture models (Keene et al, 2014) to assess the impact of different assumptions about the statistical behavior of post-withdrawal outcomes. The post-withdrawal part of each pattern-specific distribution will be modelled using MAR and Copy Reference (CR) approaches. The MI will be carried out in the following steps:

1. Fit a Bayesian negative binomial model with a non-informative prior to the observed data with same set of covariates as in the primary analysis and obtain the posterior distributions of the event rate for both treatment arms.
2. Draw 100 independent samples from the conditional distribution of missing counts given the observed count and period of each patient with missing data based on different post-withdrawal imputation models, described below, for the treatment arms. The conditional distribution is also negative binomial.
3. The observed counts and imputed counts for each patient with missing data are summed.
4. Each 100 imputed datasets will then be analyzed using the same negative binomial regression model. Estimates from the model such as least squares means and standard errors are then combined across imputation datasets using Rubin's formula, as implemented in the MIANALYZE procedure. These and their 95% confidence interval limits are then exponentiated to obtain the estimate of ABR for each arm and the estimate of the ABR ratio and associated p-value.

MAR and CR approaches are described below:

1. Missing at Random (MAR) Approach: Post-withdrawal missing bleeding events in both fitusiran arm and on-demand arm will be imputed under the randomized arm.
2. Copy Reference (CR) Approach: The expected ABR for a patient in the fitusiran arm both pre- and post-withdrawal is assumed to be the same as that in the on-demand arm. This accounts for a gradual loss of fitusiran effectiveness post-withdrawal. If a patient in fitusiran arm has more events pre-withdrawal than expected if this patient had been in the on-demand arm, then this 'positive residual' will feed through into a higher than expected ABR in the post-withdrawal period. This is because this patient's earlier observed ABR higher than mean event rate suggests the patient has a higher propensity to have events. Post-withdrawal data in the on-demand arm are imputed under randomized arm (assumes MAR approach).

The efficacy analysis based on treatment policy strategy may serve as sensitivity analyses for the primary efficacy analysis based on on-treatment strategy. It is important to note that the estimand based on on-treatment strategy (the primary efficacy analysis) is considered most relevant and applicable in assessing and reporting clinical efficacy of fitusiran vs. on demand treatment.

Per-protocol analysis

Efficacy analysis will be repeated on the per-protocol analysis set as defined in [Section 4](#).

Zero-inflated negative binomial model

To address the concern of potential excessive zero bleeding events, the above on-treatment and treatment policy efficacy analyses will be repeated using the zero-inflated negative binomial model and the results will be presented if model converges.

Covid-19 related sensitivity analysis

To address the impact of Covid-19, the above on-treatment and treatment policy efficacy analyses in the treatment and efficacy periods will be repeated on the Covid-19 unaffected set as defined in [Section 4](#). In addition, a sensitivity analysis based on on-treatment strategy will be performed excluding the bleeding events in the period of missing at least two fitusiran doses in consecutive scheduled visits due to Covid-19 which is defined as one month after last dose (ie, last dose date + 28 days) before missing doses due to Covid-19 to one month after starting of re-dosing (ie, first re-dose date + 28 days). The same negative binomial model as in the primary analysis will be used.

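### Copy Reference imputes a constant post-withdrawal bleeding rate, not a gradual loss of effect, and no planned bleeding-rate imputation covers fast or full loss

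*SAP*

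**What the plan says.** SAP 6.3.1.2 runs a supportive treatment-policy analysis and then tests its MAR assumption for bleeds not collected after study withdrawal. The post-withdrawal part "will be modelled using MAR and Copy Reference (CR) approaches". Missing counts are drawn from a negative binomial distribution conditional on each patient's own observed count and observed time. Under CR, a fitusiran patient is given the on-demand mean for the time before withdrawal as well as after it. The SAP then states: "This accounts for a gradual loss of fitusiran effectiveness post-withdrawal". It explains how a patient with more bleeds than expected (a positive residual) is imputed at a higher rate. It does not discuss the opposite case, and it gives no speed or size for the loss.

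The planning values are in SAP 5.1: "Assuming a mean ABR of 18 with standard deviation (SD) = 14 in the on-demand arm" and "a mean ABR of no more than 4 with SD = 6 in the fitusiran treatment arm", with 120 patients randomized and 20% dropout.

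**The concern.** Two features of the model conflict with the description. First, the patient's gamma frailty is fixed, so nothing in the conditional distribution depends on time since withdrawal. Second, because CR applies the on-demand mean to the time on drug as well, a patient doing well on fitusiran looks like someone who would also have bled little on demand. With planning rates of 4 and 18, that negative residual is the typical case. Over 120 days the on-demand mean predicts 18 × 120/365.25 = 5.9 bleeds, while a typical fitusiran patient has 1.3.

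The interpretation is at stake. CR is the only non-MAR scenario for the bleeding endpoints, so agreement between MAR and CR could be taken as robustness to a loss of effect more severe than anything imputed.

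**Working it through.** **The plan's own figure.** SAP 5.1 states: "it is projected that the study will have greater than 90% power for testing treatment difference in mean ABRs". With 32 and 64 evaluable patients, the variance of the log rate ratio is (14/18)²/32 + (6/4)²/64 = 0.0189 + 0.0352 = 0.0541, so SE = 0.2325. Then |ln(4/18)|/SE = 1.504/0.2325 = 6.47, and power exceeds 99.9%. 96/0.8 = 120. The planning figures reproduce.

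**Dispersion (derived; the documents do not state it).** Day 29 to Day 246 is 218 days, or 0.597 years. Solve SD² = rate/0.597 + rate²/k for the gamma shape k:
- On-demand: 196 = 30.2 + 324/k, so k = 1.95.
- Fitusiran: 36 = 6.7 + 16/k, so k = 0.55.
- One shape fitted to both arms, as the SAP's model does: about 0.94 to 1.0.

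**CR rate for one leaver.** The conditional mean rate is (k + y)/(k/18 + t). With y = 4t, the share of the 14-bleed benefit kept is t/(k/18 + t), and the rate is 18 − 14 × share. Covariates are ignored.

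| Observed days before withdrawal | k = 1.95: rate (share kept) | k = 0.94: rate (share kept) |
|---|---|---|
| 14 | 14.3 (26%) | 12.1 (42%) |
| 28 | 12.2 (41%) | 9.7 (59%) |
| 60 | 9.6 (60%) | 7.4 (76%) |
| 120 | 7.5 (75%) | 5.9 (86%) |
| 180 | 6.5 (82%) | 5.3 (90%) |

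These are days of observed follow-up. In the efficacy-period analysis they count from Day 29. More than half the benefit is kept once t exceeds k/18 years: about 40 days at k = 1.95 and 20 days at k = 1.

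**Constancy.** For k = 1 and withdrawal after 109 observed days, simulated imputed rates in four successive 28-day blocks were 6.19, 6.22, 6.20 and 6.18. A patient with no bleeds in those 109 days is imputed at 1/(1/18 + 0.298) = 2.8 a year, below the fitusiran mean of 4.

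**Effect on the rate ratio.** Assume withdrawal times uniform over the 218 days, so a leaver misses half the period on average. With dropout d and R the share kept, averaged over missing time, the ratio is [4 + d × ½ × 14 × (1 − R)]/18. For d = 20%:
- MAR (R = 1): 4/18 = 0.222.
- CR, k = 1.95: R = 0.56, ratio 0.257.
- CR, k = 1: R = 0.685, ratio 0.247.
- CR, k = 0.55: R = 0.78, ratio 0.239.
- Full loss at withdrawal (R = 0): 5.4/18 = 0.300.

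CR's share of the full-loss shift is 1 − R, or 22% to 44%. A linear loss, which really is gradual, gives 0.290 over 28 days, 0.274 over 84 days and 0.253 over 183 days. At 40% dropout the ratios are 0.222 (MAR), 0.257 to 0.291 (CR) and 0.378 (full loss).

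**Significance.** In 150 simulated trials with 20 imputations each, CR and full loss were significant in every trial at 20% and 40% dropout. The weakest full-loss result at 40% had z = −2.01. A cruder covariance approximation left CR at 100% and put full loss at 98% and 95%.

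**The case against.** The mechanism is disclosed. The SAP says that it conditions on the observed count and time and that the on-demand mean applies before and after withdrawal, so a statistician can derive the negative-residual case by symmetry. This stands: the fault lies in one interpretive sentence and an omitted case, not in a hidden method.

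A reader might infer that CR is far weaker than the SAP describes. The documents do not support that, because the SAP commits to no speed or size of loss. Protocol 4.2 allows about six further months of antithrombin follow-up, so slow loss is a fair reading of gradual. A 183-day linear loss gives 0.253, inside the CR range of 0.239 to 0.257.

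A reader might also infer that loss of effect is never tested. It is tested in part: CR raises a leaver's rate above 4 and moves the ratio above 0.222. Nor is most of the benefit kept for everyone. Leavers with 14 to 28 observed days keep 26% to 59%. Patients with no data after Day 28, whom SAP 6.3.1.1 sends to this imputation, fall in that range.

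The scope is limited. This is a sensitivity check on a supportive analysis, and patients who stop drug are encouraged to stay and keep recording bleeds. MAR plus CR arguably meets the protocol's request in 8.2.5.1 for different missing-data mechanisms. Haem-A-QoL has its own worst-score imputation in SAP 6.3.2.4. None of this makes the quoted sentence correct or supplies a fast-loss or full-loss scenario for bleeding.

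**Conclusion.** The concern holds in limited form. The stated property of CR is wrong for the SAP's model: the imputed rate is constant over missing time and depends on the time already observed on drug. CR is a partial-loss scenario. On average it is close to a slow six-month loss, and it is clearly milder than fast or full loss. At 20% dropout the expected ratio is about 0.24 to 0.26, against 0.222 under MAR and 0.300 under full loss.

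These sizes rest on the planning means and SDs, a derived shape of 0.55 to 1.95, evenly spread withdrawal and no covariates. The documents give neither the dispersion nor the withdrawal timing. The constancy of the rate needs none of these assumptions. What could mislead is the sensitivity estimate and how it is read. Statistical significance is not expected to change at planning values.

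**What to change.** In SAP 6.3.1.2:
- Replace the sentence on gradual loss with the conditional-mean formula. State that a negative residual lowers the imputed rate below the on-demand rate, and more so the longer the observed time on drug.
- Keep CR and label it the intermediate, partial-loss case.
- Add at least one harsher scenario for the bleeding rate. One option is jump-to-reference: estimate the patient's frailty under the fitusiran mean, then impute at λO(k + y)/(k + λF·t), where λF is the fitusiran rate. The other is a delta series that multiplies the fitusiran post-withdrawal rate until significance is lost.

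The cost is a few lines of SAP text and extra runs of the planned 100-imputation program, with no new data. The downside is a less favourable worst-case ratio, about 0.30 instead of 0.24 to 0.26 at planning values with 20% dropout.
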